## 9. Safety and Tolerability Analysis

Safety will be evaluated from reported AEs, changes in clinical laboratory values, changes in vital signs, electrocardiogram (ECG) and physical examination results. Safety data will be summarized by stage and group as described in Section 4.1.

All safety analyses will be performed on the SAF.

### 9.1. Adverse Events

The number, percentage and incidence rate of subjects reporting treatment emergent AEs (TEAEs), grouped by MedDRA system organ class (SOC) and preferred term (PT) (coded using MedDRA v21.1), will be tabulated by Stage, and treatment group. In the case of multiple occurrences of the same TEAE within the same subject and Stage, a subject will only be counted once for each PT or SOC. Similar methods will be used to provide summaries further reported by severity and relationship. In the summaries reporting severity and relationship to study medication the event with the maximum severity and strongest relationship will be reported, respectively. For these analyses, missing severity and relationship will be imputed as described in Section 6.1.3.2.

The frequency, percentage, and incidence rate of subjects reporting TEAEs, will be reported as described for the following summaries:

- TEAEs by SOC and PT
- TEAEs by SOC, PT, and maximum severity
- Treatment-related TEAEs by SOC and PT
- Treatment-related TEAEs by SOC, PT, and maximum severity

An overall summary of TEAEs, TEAEs leading to discontinuation of study, serious TEAEs, Severe or life-threatening TEAEs, and fatal AEs will be reported. This summary will also be reported for treatment-related TEAEs. Overall summaries for TEAEs and

treatment-related TEAEs by maximum severity will also be provided. The number of total events at each level of TEAE reporting will also be used in the calculation of incidence rate per subject-years of study participation given the specified Stage and reporting treatment period (total events/total patient-years included in the reported treatment period). In general, the duration of the reported treatment period is based on the amount of time a subject has taken the assigned drug within each Stage of reporting for a specified treatment; this is described in more detail in Section 6.1.4.

Missing and partially missing AE start and/or stop dates will be used to determine TEAE status for reporting, according to the specifications described in Section 6.1.5.

In the AE data listings, all AEs will be displayed. AEs that are not treatment-emergent will be flagged.

## 9.2. Adverse Events of Interest

The following are AEs of interest.

- Suicidality (ideation or attempt)
- Abuse and/or dependency events (drug & alcohol)
- Dissociative experience events
- Depression (or worsening depression)

The following AEs are also of potential clinical interest

- Eating disorder
- Nightmares (or worsening nightmares)
- Anxiety (or worsening anxiety)
- Panic attack
- Self-injurious behavior
- Aggressive behavior toward others
- Negative social events (e.g. loss of job, separation from significant other)

A summary of incidence rates (frequencies and percentages) by SOC, and preferred term will be prepared for all adverse event of interest listed above. The summary will be presented for each Stage as described in Section 9.1.

### 9.2.1. Adverse Events Leading to Discontinuation of Study

A summary of incidence rates (frequencies and percentages) of TEAEs leading to discontinuation of study, by SOC, and preferred term will be prepared. The summary will be presented by each Stage, as described in Section 9.1. No inferential statistical tests will be performed.

A data listing of AEs leading to withdrawal/discontinuation of study will also be provided, displaying details of the event(s) captured on the CRF.

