### **12.5.7. Action Taken for Adverse Events**

For each reported AE, the action taken must be evaluated and recorded on the eCRF according to the following criteria:

- No action taken
- Concomitant medication taken
- Hospitalization or prolongation of hospitalization
- Discontinued study
- Non-drug therapy
- Other (specify)

The investigator must also document on the eCRF the action taken with study drug (as a result of a given AE) according to the following criteria:

- Dose not changed
- Study drug withdrawn

- Not applicable
- Unknown

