### **14.10.1. Adverse Events**

Adverse events will be categorized by system organ class (SOC) and preferred term with the Medical Dictionary for Regulatory Activities. Summary tables for TEAEs will include numbers and percentages of subjects experiencing AEs by SOC and preferred term. If a subject has more than 1 AE that codes to the same preferred term, the subject will be counted only once for that preferred term. Similarly, if a subject has more than 1 AE within an SOC category, the subject will be counted only once in that SOC category. The following summary tables will be included in the clinical study report for each treatment and overall: summary of AEs, relationship of AEs to study drug, severity of AEs, SAEs, and AEs leading to study drug discontinuation.

Data listings will be provided for all AEs, AEs leading to study drug discontinuation, and SAEs.

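### The protocol promises a table and listing of AEs leading to study drug discontinuation; the SAP selects all such outputs on discontinuation of the study instead and does not declare the change (minor).

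*SAP*

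**What the plan says.** Protocol 14.10.1 lists the AE tables that the clinical study report will contain for each treatment and overall: "summary of AEs, relationship of AEs to study drug, severity of AEs, SAEs, and AEs leading to study drug discontinuation". It makes a matching commitment for listings: "Data listings will be provided for all AEs, AEs leading to study drug discontinuation, and SAEs".

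The SAP reports AE-related discontinuation in three places, each time by departure from the study:

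- SAP 9.1, overall summary: "An overall summary of TEAEs, TEAEs leading to discontinuation of study, serious TEAEs, Severe or life-threatening TEAEs, and fatal AEs will be reported".
- SAP 9.2.1, table: "A summary of incidence rates (frequencies and percentages) of TEAEs leading to discontinuation of study, by SOC, and preferred term will be prepared".
- SAP 9.2.1, listing: "A data listing of AEs leading to withdrawal/discontinuation of study will also be provided".

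Protocol 12.5.7 describes what is recorded for each AE. One item is the action taken for the event, and "Discontinued study" is one of its categories. A second item follows: "The investigator must also document on the eCRF the action taken with study drug (as a result of a given AE"). Withdrawal of study drug is a category of that second item.

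SAP 11 gives five changes from the protocol's planned analysis. None concerns this selection.

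**The concern.** The protocol's table answers how often an adverse event led to stopping the capsules. The SAP's table answers how often an adverse event led to leaving the trial. With two separate eCRF items, the answers can differ. A subject could stop drug for an AE near the end of a stage and still attend the closing visit. Or the event could be coded as drug withdrawn while the general action item carries something else, such as a concomitant medication.

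Safety and tolerability is part of the study's overarching goal and a secondary objective, and stopping treatment for an AE is a direct measure of tolerability. At stake are a protocol reporting commitment that the SAP does not carry through, and possibly an undercount of the event that the protocol names, in small active groups.

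**Working it through.** The plan gives no rate for this event, so there is no figure of its own to reproduce. The check is a comparison of texts, followed by simple arithmetic on what one subject would weigh.

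**Step 1. Outputs side by side**

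| Output | Protocol 14.10.1 | SAP 9.1 and 9.2.1 |
|---|---|---|
| Row in overall summary | not itemised | discontinuation of study |
| Table | study drug discontinuation | discontinuation of study |
| Listing | study drug discontinuation | discontinuation of study |

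The protocol promises two outputs on stopping drug. The SAP text specifies none on that criterion and three on leaving the study.

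**Step 2. Are these two names for one event?** Not in the data. Protocol 12.5.7 puts them in separate items, and the second is required in addition to the first. The protocol also treats them in separate sections: 10.5 for stopping drug and 8.4 for withdrawal from the study.

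**Step 3. Which events would be lost?** Those with drug withdrawn recorded but study discontinuation not recorded. They would be missing from all three SAP discontinuation outputs. They would still be counted in the SAP 9.1 tables by SOC and PT, severity and relationship, and shown in the listing of all AEs.

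**Step 4. Weight of one subject.** Inputs: 156 subjects randomised 4:1:1; 15% Stage 1 dropout, taken here to apply to placebo; re-randomisation of placebo subjects 3:2:2 (Protocol 7.1 and 14.2).

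- Stage 1, per active dose: 156 × 1/6 = 26. One subject is 1/26 = 3.8%.
- Stage 1 placebo: 156 × 4/6 = 104. Entering Stage 2: 104 × 0.85 = 88.4. Per active dose: 88.4 × 2/7 = 25.3. One subject is 1/25.3 = 4.0%.
- Both stages, per dose: 26 + 25 = 51. One subject is 1/51 = 2.0%.

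**Step 5. Number of subjects missed.** The documents give no rate of stopping drug for an AE and no overlap between the two items. The number starts at zero and cannot be taken further from the text.

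**The case against.** The strongest reply is that in this trial stopping drug and leaving the study nearly coincide. Protocol 10.5, the only section on drug discontinuation, sends the reader to the withdrawal criteria in 8.4. Sections 8.4 and 13.1 withdraw subjects from the study for an AE that the investigator judges to warrant it, and 13.1 adds confirmed laboratory and QTc findings. After withdrawal there is an Early Termination visit (9.8), and no section describes follow-up off drug. This stands as an argument about size: heavy overlap is likely. It does not make the two criteria the same, and nothing in the documents rules out a gap.

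Other parts of the reply also stand:

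- The data are not lost. SAP 6.1.3 puts all recorded CRF data in listings, and SAP 7.4 summarises treatment duration and compliance by actual treatment.
- The table is descriptive, with no inferential test. The study stopping rule in Protocol 13.2 rests on the individual stopping criteria, not on this table.
- SAP 13 refers to a separate shells document that is not available here. It might contain the table, but the SAP text does not specify it.
- The SAP does not say which field drives the 9.2.1 outputs. A subject whose disposition reason is withdrawn consent or loss to follow-up could still have an AE coded as leading to study discontinuation, so such subjects are not necessarily missed.

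A reader might infer that AE-related drug stops vanish from the trial's principal tolerability reporting, or that the comparison of active with placebo is biased. The documents support neither. No table is given that principal status, the events remain in the general TEAE tables, and nothing shows that any loss would differ by arm.

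**Conclusion.** The mismatch holds on the text. The SAP replaces the protocol's criterion in every AE-discontinuation output and does not declare it in SAP 11. The consequence is conditional: a TEAE for which drug was stopped but study discontinuation was not recorded would be absent from those summaries, although still reported elsewhere. The number affected is unknown and may be zero. Each missed subject would be about 4 percentage points in a stage table for one active dose, or about 2 points of the roughly 51 exposed per dose over both stages. These weights assume the planned 156 subjects and the planned dropout; they are not estimates of an error. No efficacy result depends on this. Severity: minor.

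**What to change.** In SAP 9.1, add a row to the overall summary for TEAEs where the action taken with study drug was withdrawal. In SAP 9.2.1, add an SOC/PT table and a listing on the same selection, by stage and actual treatment. Keep the discontinuation-of-study outputs as separate items, and state which eCRF item selects each set. If the sponsor prefers to report study discontinuation only, the replacement should be declared and justified in SAP 11, with the protocol commitment addressed there.

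The cost is one row, one table and one listing from a field that the eCRF already collects. If the two sets prove identical, the extra table is redundant but does no harm.

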## 9.2.2. Deaths and Serious Adverse Events

Any deaths that occur during the study will be listed.

Serious adverse events will be listed and tabulated by SOC and PT; the summary will be presented by each Stage, as described in Section 9.1. A summary of fatal TEAEs will also be provided.

## 9.3. S-STS

Data collected for S-STS will be summarized using descriptive statistics. Change from baseline will also be calculated and summarized in the same manner. All S-STS data will be provided in the data listings.

A summary of subjects with a score of 3 or 4 on questions 2 to 8 and 13 will be presented by stage and treatment group.

## 9.4. Clinical Laboratory Evaluations

Laboratory test results from hematology, serum chemistry, and urinalysis will be summarized descriptively (counts and percentages for categorical parameters) by treatment group, Stage and time point as both observed values and change from baseline values. Proportion of subjects with values < LLN and >ULN by treatment group, Stage and time point will be presented in summary tables.

The number of subjects with clinical laboratory values below, within, or above the normal range in relation to baseline will be tabulated for each clinical laboratory analyte by Stage and treatment group (bi-directional shift table) and visit. For those shift table, the most extreme post-baseline value will be used.

Urine drug screen, alcohol test and urine pregnancy test results will be presented in listings.

Potentially Clinically Significant (PCS) Laboratory Tests are defined as below

**Table 2 PCS criteria for lab tests**

Serum Chemistry	Alkaline Phosphatase (ALP)	> 2 x ULN
Serum Chemistry	Alanine Aminotransferase (ALT)	> 3 x ULN
Serum Chemistry	Aspartate Aminotransferase (AST)	> 3 x ULN
Serum Chemistry	Blood Urea Nitrogen (BUN)	> 1.5 x ULN
Serum Chemistry	Creatinine	>1.5 x Baseline or > 1.5 x ULN
Serum Chemistry	Gamma-Glutamyl Transferase (GGT)	> 3 x ULN
Serum Chemistry	Lactate Dehydrogenase (LDH)	> 3 x ULN

Serum Chemistry	Total Bilirubin	> 2 x ULN
Hematology	White Blood Cell Count	$\leq 2.8 \ 10^9/L$
Hematology	Absolute Neutrophils Count	$<1.5 \ 10^9/L$

Frequency distributions of the clinical laboratory tests of interest listed above will be summarized for PCS values at any post-baseline visit.

Evaluation of potential Drug-Induced Serious Hepatotoxicity (eDISH) will also be done by plot.

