### **3.5. Method of Assigning Subjects to Treatment Groups**

On Day 1, subjects will be randomized to receive placebo, NYX-783 50 mg QD, or NYX-783 10 mg QD in a 4:1:1 ratio, respectively. Placebo responders and placebo non-responders (CAPS-5 total score reduction from baseline  $\leq 35\%$  and total CAPS-5 total score  $\geq 26$  at Week 4) will be identified at the completion of Stage 1 (Weeks 1-4) in a blinded fashion; then, each group (i.e., placebo responders and placebo non-responders) will be re-randomized in a blinded fashion to placebo, NYX-783 50 mg QD, NYX-783 10 mg QD in a 3:2:2 ratio, respectively, for Stage 2 (Weeks 4-8).

treatment. Subjects who received active treatment during Stage 1 will receive placebo in Stage 2.

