## 4. Statistical Analysis and Reporting

### 4.1. Introduction

Data processing, tabulation of descriptive statistics, calculation of inferential statistics, and graphical representations will be performed primarily using SAS (release 9.4 or higher).

Continuous (quantitative) variable summaries will include the number of subjects (n) with non-missing values, mean, standard deviation (SD) (or standard error (SE) if appropriate), median, minimum, and maximum. Confidence intervals (CIs) will be added if appropriate.

Categorical (qualitative) variable summaries will be based on frequencies and percentages.

Unless stated otherwise, efficacy data for endpoints included in mixed effects repeated measures model (MMRM) analyses (groups [1], [2], [3], [7], [8], and [9]) will be summarized by visit and treatment group (Placebo, NYX-783 10 mg QD, NYX-783 50 mg QD) to allow for summary data treatment comparisons as per model inference.

Efficacy data for Stage 2 groups [4], [5], [6], [10], and [11] will be presented separately.

Unless stated otherwise, safety data will be summarized by Stage and treatment group (Placebo [as Placebo Only and Placebo Stage 2, separately], NYX-783 10 mg QD, NYX-783 50 mg QD); data presented by visit will be displayed based on the treatment group which applies at onset for AEs/collection date.

The minimum and maximum will be reported with the same degree of precision (i.e., the same number of decimal places) as the observed data. Measures of location (mean and median) will be reported to 1 degree of precision more than the observed data and measures of spread (SD, SE) will be reported to 2 degrees of precision more than the observed data.

Percentages will be presented to 1 decimal place, unless otherwise specified.

Unless otherwise indicated, all statistical tests will be conducted at a 0.10 significance level using one-sided tests and p-values will be reported. Corresponding 80% CIs (the interpretation of which is equivalent to a one-sided 90% CI when restricted to a single bound) will be presented.

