## 5. Analysis Populations

The following analysis populations are planned for this study. As per protocol, the 50mg QW group will not be included in analysis population. Main efficacy and safety data for those subjects will be listed.

- **Safety Population (SAF):** The SAF consists of all randomized subjects who receive at least one dose of study drug (active or placebo). SAF inclusion and reporting will be evaluated separately for each Stage so there will be a safety set defined for Stage 1 (randomized subjects who receive at least one dose of study drug (active or placebo) during Stage 1 and a safety set defined for Stage 2 (randomized subjects who receive at least one dose of study drug (active or placebo) during Stage 2). Subjects in the SAF will be analyzed according to the treatment they actually received. For definition of actual treatment see Section [6.1.4](#). Unless otherwise specified, all safety analyses will be conducted on the Safety Population.
- **Intent-To-Treat (ITT) Population:** The ITT Population will consist of all randomized subjects. Subjects in the ITT Population will be analyzed according to the treatment they are assigned at randomization. The primary efficacy analysis will be performed on the ITT Population. Unless otherwise specified, all other efficacy analyses also will be conducted on the ITT Population. Subject data for each Stage is included in ITT analyses based on the availability of randomization assignments. As efficacy results are also presented by Stage, an ITT Stage 1 population will be created (all randomized subjects) and an ITT Stage 2 population will be created (all randomized subjects entering Stage 2).
- **Modified Intent-To-Treat (mITT) Population:** The mITT Population will consist of all ITT subjects who received at least 2 weeks of study drug and had at least one post-dose measurement of CAPS-5 (CAPS-5 questionnaire must be complete.) Subjects in the mITT Population will be analyzed according to the treatment they are assigned at randomization. This analysis population will serve as sensitivity analysis for primary efficacy analysis. As efficacy results are also presented by Stage, a mITT Stage 1 population will be created (all mITT subjects) and a mITT Stage 2 population will be created (all mITT subjects entering Stage 2).

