**Table 3 PCS criteria for vital signs**

Supine Systolic Blood Pressure	$\leq 90$ and decrease $\geq 20$ mm Hg; $\geq 180$ and increase $\geq 20$ mm Hg
Supine Diastolic Blood Pressure	$\leq 50$ and decrease $\geq 15$ mm Hg; $\geq 105$ and increase $\geq 15$ mm Hg
Supine Heart Rate	$\leq 50$ and decrease $\geq 15$ bpm; $\geq 120$ and increase $\geq 15$ bpm
Body Weight	Change(increase or decrease) from Baseline $\geq 7\%$
Respiratory Rate	$<12$ and $>20$ per minute

Frequency distributions of the vital signs of interest listed above will be summarized for PCS values at any post-baseline visit.

Physical Examinations will be listed.

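### The laboratory PCS table in SAP 9.4 has no pre-dose condition, so a subject already beyond a limit counts as a post-baseline case in Stage 1 and again in Stage 2

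*SAP*

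**What the plan says.** SAP 9.4 and Table 2 set PCS limits for ten laboratory analytes. The counting rule is: "Frequency distributions of the clinical laboratory tests of interest listed above will be summarized for PCS values at any post-baseline visit". It places no condition on pre-dose PCS status, on worsening or on the denominator. Nine of the ten limits are absolute. Creatinine is the only row that mentions baseline, and it does so as an alternative: ">1.5 x Baseline or > 1.5 x ULN". A subject above the absolute creatinine limit therefore qualifies whatever the baseline was.

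Table 3 (vital signs) is built differently. Blood pressure and heart rate need both a limit and a change, as in "and decrease $\geq 20$ mm Hg", and the weight criterion is "Change(increase or decrease) from Baseline". Respiratory rate in that table is an absolute limit only.

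On display, SAP 9 says "Safety data will be summarized by stage and group as described in Section 4.1", and SAP 4.1 says "safety data will be summarized by Stage and treatment group (Placebo [as Placebo Only and Placebo Stage 2, separately". SAP 5 gives each stage its own safety population; the later one is described as "a safety set defined for Stage 2 (randomized subjects who receive at least one dose of study drug (active or placebo) during Stage 2". On treatment sequence, SAP 3.5 re-randomizes Stage 1 placebo subjects 3:2:2 and adds: "Subjects who received active treatment during Stage 1 will receive placebo in Stage 2".

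**The concern.** A PCS table in a safety report is normally read as what appeared on treatment. Here it also contains what was present before treatment. Take a subject with a long-standing neutrophil count of 1.3 x 10^9/L, against a limit of <1.5. Unless the investigator or sponsor excludes that subject on judgement, the unchanged count is a PCS case in the Stage 1 column. It is a PCS case again in the Stage 2 column, under whatever is taken then.

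The SAP does apply an emergence rule to adverse events: SAP 6.1.4 assigns each event to a stage by its onset relative to that stage's first dose. Laboratory PCS values have no equivalent rule. The absolute PCS rates for small dose groups could therefore be read as drug findings when they are not.

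**Working it through.** The plan gives no figure for this rule, so there is none to reproduce. The check has three parts.

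**1. Which rows are exposed.** Table 2 was set against Protocol 8.2.

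- ALT, AST, ALP, GGT: exclusion 31 removes values above 2 x ULN at screening. The PCS limits are 3, 3, 2 and 3 x ULN. These rows are largely protected, apart from a rise between screening and Day 1.
- Creatinine: exclusion 25 (clearance below 60 mL/min, or renal disease) removes most chronic cases. It also bears on BUN.
- Total bilirubin: exclusion 31 limits direct bilirubin only.
- White cells, neutrophils, LDH: no numeric entry limit. Exclusion 29 allows exclusion for known abnormal laboratory results, but only on judgement.

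**2. Group sizes and double counting.** Inputs are N = 156, Stage 1 ratio 4:1:1, 15% Stage 1 dropout and Stage 2 ratio 3:2:2 (SAP 3.2 and 3.5).

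- Stage 1: 156 x 4/6 = 104 placebo; 156/6 = 26 per dose.
- Stage 2 from placebo: 104 x 0.85 = 88.4, split 37.9 placebo and 25.3 per dose.
- Stage 2 from active: 52 x 0.85 = 44.2, all on placebo.
- One case is 1/26 = 3.8% of a Stage 1 dose group and 1/25 = 4.0% of a Stage 2 dose group.
- If subjects with chronic abnormalities drop out at the planned rate, 85% of them are counted in both stages. Of those first counted under Stage 1 placebo, 0.85 x 4/7 = 49% are counted again under NYX-783.

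**3. Expected counts with no drug effect.** Assumption, not in the documents: a share p of entrants is persistently beyond at least one limit for white cells, neutrophils, BUN or LDH, with p from 1% to 5%. Expected cases = n x p; chance of at least one = 1 - (1 - p)^n.

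| | p = 1% | p = 3% | p = 5% |
|---|---|---|---|
| Expected, one dose group of 26 | 0.26 | 0.78 | 1.30 |
| Chance of at least one, n = 26 | 23% | 55% | 74% |
| Chance of at least one, n = 25 | 22% | 53% | 72% |
| Chance of at least one, both Stage 1 dose groups (52) | 41% | 79% | 93% |
| Subjects affected, whole trial (156p) | 1.6 | 4.7 | 7.8 |
| Table entries, both stages (156p x 1.85) | 2.9 | 8.7 | 14.4 |

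These figures pool four analytes. As an illustration, an equal split without overlap gives 0.25% to 1.25% per analyte. The chance that a given row has at least one such case among 26 is then 1 - 0.9975^26 = 6% to 1 - 0.9875^26 = 28%.

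If the table counted only subjects who were not PCS before the stage, every persistent entry above would fall to zero in both stages.

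**The case against.** The strongest reply is that nothing here biases the comparison. A reader might infer that chronic abnormalities will make NYX-783 look worse than placebo. The documents do not support that. Stage 1 has about 104 concurrent randomized placebo subjects and Stage 2 is re-randomized, so the expected rate of chronic cases is the same p in every group. What remains is chance imbalance in small groups, in a descriptive table with no test attached.

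A reader might also infer that a Stage 1 drug effect persisting into Stage 2 contaminates the placebo rate. SAP 4.1 shows Placebo Only and Placebo Stage 2 separately. On the natural reading, subjects moved from drug to placebo have their own column. Nor does the table count every abnormal value; it counts only values beyond PCS limits.

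Other planned outputs give context: change from baseline, proportions outside the normal range, shift tables and full listings. That is partly right, and a single case can be traced. The shift tables, however, use below, within and above normal range. A subject already below range who newly crosses a PCS limit shows no shift, so new and pre-existing PCS values are not separated. The table shells are not available and might add a condition; the SAP text does not.

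Finally, an inclusive count is a defensible conservative choice, and conditioning on a non-PCS start would hide worsening in subjects already beyond a limit. That last point stands and shapes the fix.

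**Conclusion.** The point holds as a minor reporting defect. The SAP 9.4 rule mixes pre-existing with new PCS values, and the stage-by-treatment display counts persistent ones twice. The practical exposure is mainly white cells and neutrophils, with BUN, LDH and total bilirubin possible.

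The consequence is inflated absolute PCS rates and chance imbalance in groups where one case is about 4%. It is not a systematic bias between arms. The 23% to 74% range rests wholly on the assumed 1% to 5% pooled prevalence. It should not be read as the chance that any one row is affected. The 85% and 49% recount shares rest on the planned dropout rate applying equally to these subjects and on their having an on-stage sample in each stage.

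**What to change.** In SAP 9.4, tabulate treatment-emergent PCS by analyte, stage and treatment:

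- Numerator: subjects PCS during the stage whose last value before that stage's first dose was not PCS.
- Denominator: subjects with a non-PCS pre-stage value and at least one on-stage value.
- Reference value: state that, for this table, it is the last value before the stage's first dose in every group. That is Day 1 for Stage 1 and the Week 4 sample for Stage 2. The Week 4 sample is suitable because chemistry and hematology are drawn at that visit (Protocol 9.5) and Stage 2 dosing starts the next day (SAP 7.4).
- Already PCS before the stage: show these subjects in a separate row or listing with pre-stage and worst on-stage values, so that worsening stays visible.

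The reference must be stated as overriding SAP 6.1.1 for this table. That section keeps the Stage 1 safety baseline for groups 4 and 7 and uses a value before Week 4 for the other re-randomized groups. A new-PCS rule built on those baselines would treat Stage 2 placebo and active subjects differently. Hematology is not drawn at Week 2, so for white cells and neutrophils the value before Week 4 would be Day 1.

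The cost is SAP wording and minor table programming. No data collection changes.
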